Prevalence and characteristics of somatic symptom disorder in the elderly in a community-based population: a large-scale cross-sectional study in China

Assessment of Somatic Symptom in Chinese Community-Dwelling People

Protocol Number	SSSCN202011
NCT No.	NCT04815863
Date	Sep 20, 2018

STUDY PROTOCOL SYNOPSIS

Title	Prevalence and characteristics of somatic symptom disorder in the elderly in a community-based population: a large-scale cross-sectional study in China
Sponsor	Investigator-Initiated Trial (IIT)
Primary Objectives	
 1. to clarify the prevalence of somatic symptom disorder (SSD), depressive disorders, and anxiety disorders in the elderly in China; 2. to identify physical and psychological differences between the elderly and non-elderly; 3. to explore risk factors for SSD in the elderly.

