Study Design	
This prospective cross-sectional study (Assessment of Somatic Symptom in Chinese Community-Dwelling People, ClinicalTrials.gov identifier NCT04815863, registered on 06/12/2020) is a multicenter registry conducted in Shanghai, China, under the supervision of the Shanghai Association of Chinese Integrative Medicine.
 
A multistage and stratified systematic sampling technique will be used to choose representative districts from sixteen districts in Shanghai, which are then divided into low, medium, and high economic levels according to the per capita gross domestic product of each district in 2018. Eleven districts will be selected proportionally and randomly and represented by 105 community health service institutions. The study was approved by institutional review committees at each center. The study is compliant with the 1975 Declaration of Helsinki guidelines.
 
(1) assessment of somatic symptom disorder (SSD)
 
The Somatic Symptom questionnaire is self-administered with an abbreviated 20-item measure. Briefly, it is composed of four dimensions: physical disorders, depressive disorders, anxiety disorders and depressive and anxiety disorders. Half of the items ask about physical complaints (one item per body system). SSS-CN scores ranging from 20 to 29, 30–39, 40–59 and ≥ 60 correspond to normal, mild, moderate and severe SSD, respectively.
 
(2) assessment of depressive and anxiety disorders
 
All participants will be assessed for depressive and anxiety disorders according to the PHQ-9 and GAD-7, which evaluate the frequencies at which certain symptoms had been experienced over the last two weeks, ranging from 0 ('not at all') to 3 ('nearly every day'). The cutoff values are listed below. For PHQ-9, scores of 5–9 indicate mild depressive disorder, 10–14 indicate moderate depressive disorder, 15–19 indicate moderately severe depressive disorder and ≥ 20 indicate severe depressive disorder. For GAD-7, scores range from 0 to 21, with scores of 5–9, 10–14, and ≥ 15

	
representing mild, moderate, and severe anxiety symptom levels, respectively.
 
(3) sociodemographic and clinical characteristics
 
Sociodemographic data, including age, gender, level of education and marital status, will also be collected. A semi-structured questionnaire concerning clinical characteristics will be administered to survey participants' medical and medication histories.

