Number of Subjects	
Enrollment: 9110 [anticipate]
 
Elderly group: 6874 [anticipate]
 
Non-elderly group: 2236 [anticipate]

Enrollment Criteria	
Inclusion criteria were:
 
(1) voluntary participation and provision of written consent to participate in the study's evaluation and assessment;
 
(2) completion of the SSS-CN questionnaire, Patient Health Questionnaire-9 (PHQ-9) and Generalized Anxiety Disorder-7 (GAD- 7) questionnaires.
 
Exclusion criteria were :
 
(1) patients lacking self-assessed abilities or who refused to participate;
 
(2) patients who have been previously confirmed to have serious mental disorders, mental retardation, or dementia;
 
(3) patients with cancer or central nervous system diseases;
 
(4) patients with any missing data within questionnaire items or with more than one item missing from sociodemographic information;
 
(5) patients with any medical conditions that in the opinion of the investigators will not be appropriate to participate in the study.

Safety Assessment	Adverse events were not required in this study protocol.
Endpoints	
1. Number of Participants With Somatic Symptoms Disorder
 
2. Number of Participants With Somatic Symptoms Disorder Accompanied With Anxiety
 
3. Number of Participants With Somatic Symptoms Disorder Accompanied With Depression

Statistical Analysis	
Descriptive statistics for each group, such as counts and percentages (%) for non-continuous variables, will be reported for all sociodemographic and clinical characteristics. The prevalences of SSD of various severities for different genders and for participants diagnosed with depressive and anxiety disorders will be calculated. In order to assess whether SSD, depressive and anxiety disorders are associated with aged groups and whether depressive and anxiety disorders are associated with the severity of SSD, binary logistic regressions will be performed, adjusting for gender, educational level (middle school and below, high school, college, master and above), marital status (never married, married, divorced, widowed), hypertension (yes/no), diabetes mellitus (yes/ no), CV disease

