	
(yes/no), endocrine and metabolic disease except DM (yes/no), other diseases (yes/no), surgery (yes/no) and antipsychotic intake (yes/no) in all models.
 
Univariate analyses and binary logistic regression models will be used to assess the effects of sociodemographic factors and clinical characteristics on SSD in the non- elderly and elderly. Categorical sociodemographic and clinical variables will be analyzed by chi-square test. Binary logistic regressions will be performed using SSD (yes/no) as the dependent variable, adjusting for gender, educational level, marital status, and antipsychotic intake.
 
Fisher's exact test was used instead of the chi-square test only when one or more expectations for each cell of the 2-by-2 tables was below 5. A significance level was set at a p-value < 0.05 (two-tailed). Missing data were imputed with a multiple imputation approach. All statistical analyses were performed with SPSS 22 (IBM SPSS Statistics for Windows, Version 22.0. Armonk, NY: IBM Corp).

--	---

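### Age is collected but not named in the adjustment list of the within-group SSD models, so odds ratios for age-related factors may be confounded by age

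*Combined protocol and SAP*

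**What the plan says.** The Study Design section, item (3), states: "Sociodemographic data, including age, gender, level of education and marital status, will also be collected". The Statistical Analysis section then describes two sets of logistic models.

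The first set is introduced with "In order to assess whether SSD, depressive and anxiety disorders are associated with aged groups" and also relates depressive and anxiety disorders to SSD severity. Its long covariate list ends with "other diseases (yes/no), surgery (yes/no) and antipsychotic intake (yes/no) in all models". Age is not on that list; in the age comparisons, age group is the exposure.

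The second set is meant "to assess the effects of sociodemographic factors and clinical characteristics on SSD in the" non-elderly and elderly. For it the plan says: "Binary logistic regressions will be performed using SSD (yes/no) as the dependent variable, adjusting for gender, educational level, marital status, and antipsychotic intake". It serves the third primary objective, "to explore risk factors for SSD in the elderly". The one univariate test described for these factors is: "Categorical sociodemographic and clinical variables will be analyzed by chi-square test".

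**The concern.** Of the four sociodemographic variables that the plan names as collected, gender, education and marital status are on the within-group adjustment list and age is not. Fitting the models separately by age group restricts the age range in each fit, but no cut-off or age range is stated and age still varies inside each group.

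The candidate risk factors include hypertension, diabetes, cardiovascular disease and marital status, all of which plausibly change with age. If SSD also changes with age within a group, a factor with no effect can look like a risk factor, or a real one can be hidden. What is at stake is the reading of individual odds ratios under the third objective (elderly) and in the parallel non-elderly analysis.

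**Working it through.** **Step 1: the lists side by side.**

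| Variable | Collected | Within-group SSD list | Longer list |
|---|---|---|---|
| Age | yes | not named | not named (age group is the exposure in the age comparisons) |
| Gender | yes | yes | yes |
| Educational level | yes | yes | yes |
| Marital status | yes | yes | yes |
| Antipsychotic intake | through medication history | yes | yes |

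Even if the words closing the longer list are read to cover every model in the plan, age is still missing.

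**Step 2: a hand check of the possible size, without covariates.** From the documents: 6874 elderly, 2236 non-elderly, two-sided 0.05. Everything else is assumed: disease prevalence 30% with log-odds a = 0.05 per year of age; SSD prevalence 20% with log-odds b = 0.02 per year; true disease effect zero. Age SD: 5.3 or 8.7 years in the elderly (60–90, truncated normal or uniform); 9.3 or 11.8 in the non-elderly (18–59).

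Diseased and disease-free people differ in mean age by about a × SD², so the spurious log odds ratio is about b × a × SD². Its standard error is about 1/√(n × 0.2 × 0.8 × 0.3 × 0.7):

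- elderly: 1/√(6874 × 0.16 × 0.21) = 1/√230.97 = 0.0658
- non-elderly: 1/√(2236 × 0.16 × 0.21) = 1/√75.13 = 0.1154

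With z = log OR / SE, the false-positive rate is Φ(z − 1.96) + Φ(−z − 1.96).

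| Group, age SD | Log OR | OR | z | False-positive rate |
|---|---|---|---|---|
| Elderly, 5.3 | 0.02 × 0.05 × 28.09 = 0.028 | 1.03 | 0.43 | 7% |
| Elderly, 8.7 | 0.02 × 0.05 × 75.69 = 0.076 | 1.08 | 1.15 | 21% |
| Non-elderly, 9.3 | 0.02 × 0.05 × 86.49 = 0.086 | 1.09 | 0.75 | 12% |
| Non-elderly, 11.8 | 0.02 × 0.05 × 139.24 = 0.139 | 1.15 | 1.21 | 23% |

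An exact large-sample fit without covariates gives nearly the same: 1.03–1.08 (7–20%) and 1.08–1.14 (11–21%).

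**Step 3: with all four planned covariates in the model.** This is a large-sample logistic fit over all combinations of age, gender, education, marital status, antipsychotic intake and one disease at a time. Further assumptions:

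- Both groups: 55% female, 3% on antipsychotics; SSD log-odds +0.3 for female, −0.1 per education level, +0.5 for antipsychotics; zero for marital status and disease.
- Elderly: education 60/25/14/1%, slope −0.04 to −0.06 per year; married/never married/divorced/widowed 68/2/5/25%, widowed slope +0.08 to +0.12.
- Non-elderly: education 30/30/35/5%; marital status 70/20/7/3% in the same order, never-married slope −0.15 to −0.25, widowed +0.08 to +0.12, divorced +0.03.

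| Factor with no true effect | OR without age | False-positive rate | SE increase when age is added |
|---|---|---|---|
| Disease, elderly | 1.03–1.07 | 7–17% | 1–2% |
| Widowed vs married, elderly | 1.05–1.15 | 10–51% | 2–8% |
| Disease, non-elderly | 1.05–1.10 | 7–13% | 2–3% |
| Never married vs married, non-elderly | 0.73–0.82 | 29–54% | 11–20% |

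The last row depends on how education is assumed to fall with age in the non-elderly; a repeat of the calculation gave 0.75–0.83 and 25–46%. The planned covariates absorb up to about 20% of the disease bias (log scale) in the elderly and about 25–40% in the non-elderly. With age added, every odds ratio returns to 1.00 and the false-positive rate to about 5%.

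**Step 4: sensitivity to the SSD age trend, elderly.**

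| SSD log-odds per year | Disease | Widowed |
|---|---|---|
| 0 | 1.00, 5% | 1.00, 5% |
| +0.01 | 1.01–1.03, 5–8% | 1.02–1.07, 6–17% |
| +0.03 | 1.04–1.10, 9–31% | 1.07–1.23, 16–85% |

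Negative trends mirror these (at −0.02, disease 0.94–0.98, 7–17%).

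**Step 5: simulation check.** With 3000 datasets per scenario and the weaker covariate slopes, false-positive rates without and with age were, for truncated-normal and then uniform ages: elderly disease 7.2% vs 5.0% and 15.8% vs 5.0%; widowed 9.5% vs 4.9% and 32.1% vs 4.7%; non-elderly disease 8.5% vs 5.2% and 12.3% vs 4.8%; never married 28.8% vs 4.6% and 44.4% vs 4.7%.

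**The case against.** The strongest reply is that age may already be in the model. The plan studies sociodemographic factors, age is listed first among them, and if all factors enter jointly the others are adjusted for it. Age might also be analysed in bands, in which case the chi-square test would cover it. This stands as a possible reading: what is shown is a gap in the stated model, not proof of an unadjusted analysis. But no sentence says that the other odds ratios are adjusted for age, and someone following the written list would leave it out.

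Other points also stand in part:

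- The third objective concerns the elderly only, so the never-married result in the non-elderly does not bear on it. In the elderly the middle-case disease bias is small.
- The high false-positive rates owe much to n = 6874. The 51% and 85% maxima for widowhood correspond to odds ratios of 1.15 and 1.23, at the steep end of the assumptions.
- The calculation enters one disease at a time. When five further assumed age-related conditions were entered jointly, the rate fell from 13–42% to 12–33% for widowed (elderly), from 36–54% to 29–41% for never married (non-elderly), and from 16% to 13% for disease (elderly, uniform ages). These starting ranges come from a separate fit with similar inputs. The bias shrinks but does not vanish.
- The age trend in SSD decides everything, and neither its size nor its sign is in the documents.

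**Conclusion.** The concern holds. Age is collected and is not named in the adjustment list of the within-group SSD models, and no other text supplies it. Whether this produces bias depends on SSD varying with age within a group, which the documents do not show either way. Under the assumed middle case the effect on a disease odds ratio in the elderly is small, while marital status is more exposed because it is itself closely tied to age. All these sizes rest on assumed age distributions, prevalences and slopes. This is a change that should be made rather than one that must be: the endpoint counts and prevalence estimates do not depend on it, but the odds ratios serving a primary objective do.

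**What to change.** Add age to the adjustment list of both within-group SSD models, as a continuous term if it is recorded in years, with a check for non-linearity. If age is already meant to enter as a sociodemographic factor, say so, and say that the other factors' odds ratios are adjusted for it. For clarity, also state whether the clinical characteristics enter one at a time or together.

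The cost is wording in the Statistical Analysis section, since no new data are needed. The models gain one or a few parameters, and intervals widen for factors strongly related to age, most of all for never married in the non-elderly.
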